7.3.3 Return to Work

Time to return to work and time to return to full work (or normal household activities if non-working), in days, will be summarized.

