### **Secondary Endpoints – Health Economic Outcomes**

All health economic endpoints are exploratory in nature.

1. Complications below that are related to the Lapiplasty® Procedure or the Lapiplasty® System Implants requiring subsequent secondary surgical interventions, defined as the following: 1) deviations/delay from normal operative plan 2) readmission to hospital 3) return to operating room 4) unscheduled visits due to complications 5) employment of home health services;
  - a. Revisions
  - b. Hardware removals
  - c. Reoperations
  - d. Supplemental fixations
  - e. Wound healing requiring surgical intervention
  - f. Infection at surgical site requiring surgical intervention
2. Time to return to work (or normal household activities if non-working), in days, while noting work status and work classification (sedentary, light work, medium work, heavy work, very heavy work).
3. Time to return to full work, in days (or full household activities if non-working), while noting work status and work classification (sedentary, light work, medium work, heavy work, very heavy work).
4. Post-operative physical therapy requirements required for recovery of the Lapiplasty® Procedure.

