**Index Procedure** – See **Section 7.2** for complete list of data collected during the Index Procedure. Concomitant procedures of the 1st ray should also be recorded. These include but are not limited to, akin osteotomy, bone graft harvest (synthetic or allogenic bone graft substitutes are not permitted), intercuneiform stabilization, traditional medial eminence resection, rongeur of the medial capsular ridge, and/or dorsal metatarsal bone resection. No concomitant procedures that alter the post-operative WB instructions are permitted (including evans and other calcaneal osteotomies, lesser TMT joint fusions, lisfranc or metatarsus adductus). Any complications during the procedure or deviations to the normal operative plans must also be recorded.

**POSAS:** See **Appendix 9**. The Patient and Observer Scar Assessment Scale will be collected per the Assessment instructions.

**Return to Weight-Bearing Activities** – The actual date that the subject was allowed to start to return to weight-bearing activities (protected WB in CAM boot, shoe and full unrestricted activities) should be recorded. The number of days from index procedure will be calculated by Clinindex. See **Section 5.3** for post-operative care and weight-bearing instructions.

**Secondary Surgical Interventions:** Any adverse event/complication that requires a subsequent secondary surgical intervention should be recorded. The reason for the subsequent surgical intervention and the action taken should be recorded. Subsequent secondary surgical interventions are defined as revisions, hardware removals, reoperations, supplemental fixations or other surgical intervention due to wound healing issues or infections at surgical site.

**Health Economic Outcomes:** The date the subject was allowed to return to work (or normal household activities if non-working), should be recorded while noting work status and work classification (sedentary, light work, medium work, heavy work, very heavy work). The date the subjects was allowed to return to full work (or full household activities if non-working), should be recorded while noting work status and work classification (sedentary, light work, medium work, heavy work, very heavy work – See **Appendix 1** for definitions). Any post-operative physical therapy requirements required for recovery of Lapiplasty® Procedure should be recorded. Any employment of home health services and the reason should be recorded.

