1.2.3 Health Economic and Safety Endpoints

All health economic endpoints are exploratory in nature.

- 1) Complications below that are related to the Lapiplasty® Procedure or the Lapiplasty® System Implants requiring subsequent secondary surgical interventions, defined as the following:
 - a) deviations/delay from normal operative plan
 - b) readmission to hospital
 - c) return to operating room
 - d) unscheduled visits due to complications
 - e) employment of home health services
 - f) revisions
 - g) hardware removals
 - h) reoperations
 - i) supplemental fixation
 - j) wound healing
 - k) infection at surgical site

- 2) Time to return to work (or normal household activities if non-working), in days, while noting work status and work classification (sedentary, light work, medium work, heavy work, very heavy work).
- 3) Time to return to full work (or normal household activities if non-working), in days, while noting work status and work classification (sedentary, light work, medium work, heavy work, very heavy work).
- 4) Percentage of subjects requiring post-operative physical therapy for recovery from the Lapiplasty® Procedure.

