6.4 Derived Variables

6.4.1 “Time To” variables

“Time to” variables such as time to follow-up, time to weight-bearing, and time to return to work will be computed in days as (date of interest - date of index procedure). “Time to” will be computed in weeks as (date of interest - date of index procedure)/7. “Time to” will be computed in months as (date of interest - date of index procedure)/30. “Time to” will be computed in years as (date of interest - date of index procedure)/365.25.

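### SAP 1.2.3 item 3 ties return to full work in non-working subjects to normal, not full, household activities, so read literally it gives them the same milestone for both return-to-work endpoints

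*SAP*

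**What the plan says.** The protocol separates the two milestones in both places where the endpoints are listed, the synopsis and section 3.0 (Health Economic Outcomes). The first endpoint is "Time to return to work (or normal household activities if non-working), in days". The second is "Time to return to full work, in days (or full household activities if non-working", followed by the closing bracket.

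Protocol 7.12 (Health Economic Outcomes) carries the distinction into data collection. For the first milestone: "The date the subject was allowed to return to work (or normal household activities if non-working), should be recorded". For the second: "The date the subjects was allowed to return to full work (or full household activities if non-working), should be recorded".

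The SAP keeps the first endpoint as it stands (1.2.3 item 2) but words the second as "Time to return to full work (or normal household activities if non-working), in days" (1.2.3 item 3). The analysis text in SAP 7.3.3 is a single sentence: "Time to return to work and time to return to full work (or normal household activities if non-working), in days, will be summarized". Its only bracket comes directly after the second time: "time to return to full work (or normal household activities if non-working", closing bracket omitted here. SAP 7.3.2 names return to work and return to full work as two outcomes but does not say what either means for a non-working subject. Full household activities are not mentioned anywhere in the SAP.

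Under SAP 6.4.1, a time-to variable "will be computed in days as (date of interest - date of index procedure", closing bracket omitted here.

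**The concern.** The SAP is what the programmer works from, and its endpoint list gives non-working subjects the same event for both endpoints. Two things would follow. First, the endpoints would no longer be distinct for those subjects. Second, the pooled summary of time to full work would combine full work in workers with an earlier milestone in non-workers, and so could look shorter than the protocol's endpoint.

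Independent reproduction by the second statistician would not necessarily expose this, because both analysts could work from the same SAP wording. Protocol 9.8 says the SAP will give a rationale for any change to the analysis, and the SAP gives none for this one.

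**Working it through.** The plan states no figure for this point, so there is nothing to reproduce. The check compares the texts and then applies the SAP's own derivation.

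**Milestone for a non-working subject, by source**

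| Source | Return to work | Return to full work |
|---|---|---|
| Protocol synopsis and 3.0 | normal household activities | full household activities |
| Protocol 7.12 (date recorded) | normal household activities | full household activities |
| SAP 1.2.3, items 2 and 3 | normal household activities | normal household activities |
| SAP 7.3.3 | one bracket, normal, placed after both times | same bracket |
| SAP 7.3.2 | named, not defined | named, not defined |

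SAP 1.2.3 item 3 is the explicit departure. It is a separate list item, and it attaches normal household activities to full work.

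**Effect on one non-working subject.** Let D0 be the index procedure date, Dn the date allowed to return to normal household activities, and Df the date allowed to return to full household activities.

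- Protocol: first time = Dn − D0; second time = Df − D0.
- SAP read literally: first time = Dn − D0; second time = Dn − D0.
- Difference between the two endpoints under the SAP: 0 days.
- SAP second time minus protocol second time: Dn − Df. This is zero or negative if full activity is not allowed before normal activity. The documents do not state that ordering, but the wording implies it.

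Working subjects are unaffected.

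**Effect on the pooled mean.** If the same subjects contribute under both definitions,

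understatement = (non-working share) × (mean of Df − Dn among non-workers).

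The documents give neither input. The values below are assumptions and serve only to show the scale:

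| Non-working share | Mean gap 0 days | 14 days | 42 days |
|---|---|---|---|
| 20% | 0 | 0.2 × 14 = 2.8 | 0.2 × 42 = 8.4 |
| 40% | 0 | 0.4 × 14 = 5.6 | 0.4 × 42 = 16.8 |

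An equally arbitrary choice, shares of 10% to 30% and gaps of 14 to 60 days, gives 0.1 × 14 = 1.4 to 0.3 × 60 = 18 days. The zero column is a real possibility: Protocol 7.12 records when the subject was allowed to resume, and a subject may be cleared for both on one date. The formula applies to the mean only. SAP section 7 also reports the median, and its shift cannot be obtained this way.

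**The case against.** The best case on the other side is that this is a copying slip with little practical effect. Protocol 7.12 requires the full-activity date, SAP 6.4.1 does not tell anyone to substitute one date for another, and SAP 7.3.2 still treats the two times as separate outcomes. A programmer with both date fields might well use the right one. That stands: the collapse of the endpoints is conditional on following the SAP definition literally. It does not make the definition right, because no other SAP text overrides item 3.

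Four stronger readings are tempting, and the documents do not support them.

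- A reader might take SAP 7.3.3 by itself as redefining full work. Its one trailing bracket can be read as loose shorthand for the household counterpart of both times. The point therefore rests on SAP 1.2.3 item 3.
- A reader might infer a known bias of some days or weeks. Every such figure rests on assumed inputs, and zero is not excluded. Neither normal nor full household activities is defined in the documents; Protocol Appendix 1 covers only work exertion levels.
- A reader might infer a deliberate redefinition. No rationale is given, and wording carried over from item 2 is at least as plausible. The SAP's entry of N/A under its summary of changes concerns revisions of the SAP itself and settles nothing.
- A reader might blame the SAP for pooling workers with non-workers. The protocol's own endpoint already does that; only the mismatch between normal and full comes from the SAP.

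**Conclusion.** The definition in SAP 1.2.3 item 3 is wrong as written. It contradicts the protocol's synopsis, section 3.0 and section 7.12, and SAP 7.3.3 does not correct it. Applied literally with SAP 6.4.1, it gives non-working subjects identical values for the two endpoints. The second value is then no longer than the protocol's, provided full activity is not allowed before normal activity.

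The size of the effect on the pooled summary cannot be determined from the documents. It depends on the non-working share and on the gap between the two recorded dates, and may be nil. Severity is low: these health economic endpoints are exploratory and are only summarized, and no power, alpha or primary-endpoint result depends on them. The correction is worth making because it is nearly free.

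**What to change.** Two edits to the SAP:

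1. In 1.2.3 item 3, change normal to full, so that the non-working counterpart of full work is full household activities, as in the protocol.
2. In 7.3.3, rewrite the sentence with two brackets: return to work paired with normal household activities for non-working subjects, and return to full work paired with full household activities for non-working subjects, both in days. Swapping the one word in the existing bracket is not enough, because it would either leave the first time without its household counterpart or attach full to both times.

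The derivation should then use the two dates recorded under Protocol 7.12. The cost is one word and one sentence, with no new data, no protocol amendment and no effect on other analyses. These edits restore agreement between the documents; they do not supply definitions of normal and full household activities, which remain undefined in both.

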7.3.4 Physical Therapy

Number and proportion of subjects requiring post-operative physical therapy will be summarized.

7.3.5 Concomitant Procedures

Number and proportion of subjects with at least one concomitant procedure, total number of concomitant procedures, and number of subjects by concomitant procedure type will be summarized using recorded procedure name.

7.4 Device and Product Experience

A product complaint is any written, electronic, or oral communication that alleges deficiencies related to the identity, quality, durability, reliability, safety, effectiveness, or performance of a device after it is released for distribution. A product complaint may or may not be associated with an AE/SAE. A listing of all reported device observations, malfunctions or failures for the Lapiplasty® System products will be generated.

7.5 Exploratory Analysis

Additional endpoints may be pursued at the time of analysis and will be exploratory in nature.

Quality Assurance of Statistical Programming

Clinical operations will independently validate the safety analyses (adverse events and clinical complications). A second statistician will independently reproduce the primary, secondary, health economic, and summary statistics.

To provide high quality code that is understandable and allows for reproduction of the analysis, the following points will be followed:

- The population to be used in a table or listing will be explicitly set at the start of a block of code that computes the output.
- All outputs will include the date and time that the output was generated, and the name of the code file that produced the analysis.
- At the start of any code file, there will be a set of comments that provide the following information: author, date, references to inputs and outputs, reference to any parent code file that runs the child code file.

Summary of Changes to the SAP

N/A

References

- ¹ Ranging from 3.6%-78% recurrence at an average of 2.4-14 years post-surgery.
- ² Shurnas PS, et al. Foot Ankle Int. 2009. 30: 865-872.
- ³ Jeuken RM, et al. Foot Ankle Int. 2016. 37:687-95.
- ⁴ Kim Y, et al. A New Measure of Tibial Sesamoid Position in Hallux Valgus in Relation to the Coronal Rotation of the First Metatarsal in CT Scans. Foot Ankle Int. 2015; 36:944-52.
- ⁵ Okuda R, et al. The Shape of the Lateral Edge of the First Metatarsal Head as a Risk Factor for Recurrence of Hallux Valgus. J Bone Joint Surg Am. 2007; 89:2163-72.
- ⁶ Okuda R, et al., Postoperative Incomplete Reduction of the Sesamoids as a Risk Factor for Recurrence of Hallux Valgus. J Bone Joint Surg Am. 2009; 91:1637-45.
- ⁷ Catanzariti AR, et al. J Foot Ankle Surg. 1999. 38:325-332.
- ⁸ Galli SH, et al. Foot & Ankle Orthopaedics. 2020. 5(2) 1-2.
- ⁹ Ray JJ, et al., Multicenter Early Radiographic Outcomes of Triplanar Tarsometatarsal Arthrodesis with Early Weightbearing. Foot Ankle Int. 2019; 40(8):955-960.

Table of Contents of Statistical Outputs

TLF #	Title
Table 1	Subject Disposition, ITT Population
Table 2	Demographic, Baseline, and Intra-Operative Characteristics, ITT Population
Table 3	Proportion of subjects with recurrence of hallux valgus deformity at 12- & 24- months post-procedure, ITT Population
Table 4	Proportion of subjects with successful correction at 6 weeks post-procedure, ITT Population
Table 5	Proportion of subjects with non-union at 12 months post-procedure, ITT Population
Table 6	Foot Swelling, ITT Population
Table 7	Time to weight-bearing, to full unrestricted activity, and to return to work, ITT Population
Table 8	Change from baseline in radiographic angular/positional alignment, ITT Population
Table 9	Change from baseline in range of motion (ROM) , ITT Population
Table 10	Change from baseline in pain at the base of the big toe as assessed by VAS, ITT Population
Table 11	Change from baseline in QoL as assessed by MOxFAQ, ITT Population
Table 12	Concomitant procedures, ITT Population
Table 13	Incision Length, ITT Population
Table 14	Metatarsalgia, ITT Population
Table 15	Lengthening, ITT Population
Table 16	Patient Satisfaction Survey, ITT Population
Table 17	Adverse events, ITT Population
Table 18	Serious adverse events, ITT Population
Table 19	Adverse events leading to death, ITT Population
Table 20	Adverse events leading to study discontinuation, ITT Population
Table 21	POSAS, ITT Population
Table 22	Change from Baseline in QoL as Assessed by PROMIS (Adult), ITT Population
Table 23	Change from Baseline in QoL as Assessed by PROMIS (Pediatric), ITT Population
Table 24	Major Protocol Deviations, ITT Population
Table 25	Summary of Clinical Complications
Listing 1	Subject Disposition, ITT Population
Listing 2	Complications, AEs, and HW Failures, ITT Population
Listing 3	All Protocol Deviations, ITT Population
Listing 4	Metatarsalgia, ITT Population

Listing 5	Radiographic Measurements, ITT Population
Listing 6	Concomitant Procedures, ITT Population
Listing 7	Device and Product Experience, ITT Population
